Related to the capacity aim, the Community Advisory Board (CAB) includes about 20 local Dan River Region health care and community partners and academic researchers. Some members of the CAB will be responsible for screening, recruit, enrollment/data collection, and program implementation and are included as study investigators. The Parent Advisory Team (PAT) includes about 15 parents who are past iChoose program participants who will serve in a similar role as a community health worker or patient navigator. They will be asked to assist in distributing recruitment materials for our open referral/enrollment process, help potential families understand both programs and timing of the intervention sessions, and ask to promote program adherence and provide a program 'safety net'. This will include contacting enrolled families and supporting their needs to successfully engage in the program. Both the PAT and CAB groups will meet monthly (e.g. using a mix of in-person and conference call meetings) and use a shared-decision making and participatory agenda meeting structure to guide all aspects of the study. As a part of this process, those who volunteer and sign informed consent will also participate in annual mixed-methods evaluation to assess capacity and engagement. Patient and stakeholder engagement and evaluation is a requirement of our funder.

To this end, we have 4 groups of participants who are in this protocol: 1) children, 2) parents of these children, 3) Community Advisory Board (CAB) members, and 4) Parent Advisory Team (PAT) members. Some members of the CAB and PAT, are both involved in the conducting the research and are research subjects who will be completing the mixed-methods evaluation as indicated in the CAB and PAT consent forms [NOTE: PAT members may NOT be simultaneously enrolled at participants in the childhood obesity treatment program].

Background

1. Provide the scientific background, rationale and relevance of this project.

A. Background

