IRB-HSR # 19748: A randomized-controlled trial to compare the reach, effectiveness and maintenance of two family-based childhood obesity treatment programs in a medically underserved region

Advisors (PHA). Since the POPS-PAT members expressed commitment to providing a social-support safety-net for *iChoose* families, are from the target population, share common demographics and cultural traits, and have already experienced a FBCO—members of the POPS-PAT have agreed to expand their roles into a formal PHA model. In combination with the proposed PHA training, *we anticipate these characteristics will promote connectedness to, and trust with targeted families and improve adherence and outcomes.*

Hypothesis to be Tested

The primary study hypotheses are:

- Effectiveness-- children in both conditions will reduce BMI-z scores significantly, when compared to baseline at 3, 6 and 12 months, but *iChoose+* reductions will be significantly larger than Family Connections,
- reach—the sample will be representative of the eligible regional population on demographic and behavioral factors
- implementation—the intervention components will be delivered with high fidelity in both conditions, but costs will be lower for Family Connections
- maintenance—a sustainability action plan will be completed to include strategies for continued delivery of *iChoose+* and/or Family Connections (outcome dependent)
- parent weight, parent/child behaviors, & tertiary outcomes that follow the same patterns as BMI z-scores
- community capacity for implementing and sustaining a locally relevant FBCO treatment and maintenance program will remain high over time

Study Design: Biomedical

1. Will controls be used?

Parent/Child Dyads: yes

Community Advisory Board: no

Parent Advisory Team: no

► IF YES, explain the kind of controls to be used.

This is comparative effectiveness trial, below is a description of the two programs:

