2. What is the study design?

- Parent/Child Dyads: comparative effectiveness trial, with randomization at the individual dyad level
- Community Advisory Board and Parent Advisory Team: capacity evaluation includes a mixed-methods, longitudinal study design

3. Does the study involve a placebo?

No

Human Participants

1) Cohorts 1-2:

Children

- **Ages:** 8-12 years
- **Sex:** male & females
- **Race:** all

Parents/caregiver

- **Ages:** ≥ 18 years
- **Sex:** male & females
- **Race:** all

2) Cohort 3:

Children

- **Ages:** 5-12 years
- **Sex:** male & females
- **Race:** all

Parents/caregiver

- **Ages:** ≥ 18 years
- **Sex:** male & females
- **Race:** all

3) All Cohorts:

Community Advisory Board and Parent Advisory Team

- **Ages:** ≥ 18 years
- **Sex:** male & females
- **Race:** all

Subjects- see below

IRB-HSR # 19748: A randomized-controlled trial to compare the reach, effectiveness and maintenance of two family-based childhood obesity treatment programs in a medically underserved region

1. Provide target # of subjects (at all sites) needed to complete protocol.

- 174 parent/child dyads
- 20 members of the Community Advisory Board
- 15 member of the Parent Advisory Team

2. Describe expected rate of screen failure/ dropouts/withdrawals from all sites.

Parent/child dyads:

- 870= Estimated number of potentially eligible study participants (parent/child dyads) determined using pilot reach data from our planning grant in which participants were identified through medical record review at SOVAH Pediatrics (formerly Children's Healthcare Center)
- 539= Total number of study participants (dyads) expected to be screened
- 496= Total number of study participants (dyads) expected to be eligible of those screened
- 174=Target sample size (dyads)
- 130= Retained sample after 12 months

We anticipate approximately 10% attrition from both the Community Advisory Board and Parent Advisory Team

3. How many subjects will be enrolled at all sites?

- 174 parents/caregivers (and 174 children with assent)
- 20 Community Advisory Board members
- 15 Parent Advisory Team members

4. How many subjects will sign a consent form under this UVa protocol?

- 174 parents/caregivers (and 174 children with assent)
- 20 Community Advisory Board members
- 15 Parent Advisory Team members

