- In addition, up to 496 subjects will be enrolled with waiver of documentation of consent. This group will include subjects who signed written consent for the main study, and subjects who completed the telephone survey but did not enroll in the main study.

5. Provide an estimated time line for the study.

For parent/child dyads in the comparative effectiveness trial:

- Cohort 1= intervention 6/2017-5/2018 (w/ 3-, 6-, & 12 months f/u)
- Cohort 2= intervention 4/2018-3/2019 (w/ 3-, 6-, & 12 months f/u)
- Cohort 3= intervention 2/2019-1/2020 (w/ 3-, 6-, & 12 months f/u)

- Year 1: 66% enrolled, 33% completed
- Year 2: 100% enrolled, 66% completed

IRB-HSR # 19748: A randomized-controlled trial to compare the reach, effectiveness and maintenance of two family-based childhood obesity treatment programs in a medically underserved region

- Year 3: 100% completed

For both the Community Advisory Board and Parent Advisory Team, 100% enrolled in Year 1; mixed-methods evaluation at end of each study year

Inclusion/Exclusion Criteria

1. List the criteria for inclusion

Cohorts 1-2:

Parent/child dyads in the comparative effectiveness trial, families are eligible to participate if they

- have a child between -12 years old with a BMI percentile that is 85% or greater for their age and gender
- live in the Dan River Region
- are English speaking
- parents/caregivers ≥ 18 years of age

Community Advisory Board members were identified and named when the PCORI application was submitted:

- Representatives from organizations in the Dan River Region who have a child-focused organizational mission, invited as a stakeholder
- ≥ 18 years of age
- Willing and able to provide informed consent

Parent Advisory Team members:

- Parent who previously participated in a childhood obesity program and/or are the parent of a child ages 8-12 years of age
- ≥ 18 years of age
- live in the Dan River Region

Cohort 3:

Parent/child dyads in the comparative effectiveness trial, families are eligible to participate if they

- have a child between 5-12 years old with a BMI percentile that is 85% or greater for their age and gender
- live in the Dan River Region
- are English speaking
- parents/caregivers ≥ 18 years of age

IRB-HSR # 19748: A randomized-controlled trial to compare the reach, effectiveness and maintenance of two family-based childhood obesity treatment programs in a medically underserved region

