Secondary Aim #1: Reach/representativeness will be analyzed following the recommendations of Glasgow et al.⁹⁰ Participation rate will be calculated as total n enrolled/ total n of eligible participants exposed to recruitment. To improve the comparison of representativeness we will, using a similar multi-level mixed effect logit models as presented above, create a summary effect size (ES) for differential characteristics by using the median ES across the comparisons of demographic, health, and behavioral information of participants versus those declining participation. (Using the median rather than the mean will minimize the influence of outliers). The median ES will then be subtracted from the participation rate to provide a summary measure of reach. Summary descriptive statistics reporting rates and cost of completion of in-person and IVR follow-ups will be computed for implementation indicators. Fidelity will be assessed as proportion of the intervention that is delivered as intended across intervention components based on IVR data and delivery agent fidelity checklists. These data will be reported descriptively and in concert with cost data. A concurrent mixed methods design will be used to collect quantitative and qualitative data collected on implementation and triangulated for interpretation.¹⁰⁰ Finally, summary RE-AIM metrics will be calculated as detail by Glasgow et al.

Secondary Aim #2: Using mixed methods,¹⁰⁰ quantitative capacity dimensions will be analyzed using repeated measures ANOVA, accounting for differences between community and academic members. Interviews will be transcribed. A minimum of two members will code meaning units from each transcript using NVIVO and a hybrid inductive-deductive analysis approach to identify emergent themes related to capacity dimension.¹⁰¹⁻¹⁰³

Secondary Aim #3: Similar multi-level mixed effect models as in primary aim 1 will be used. The dependent variables will be family eating behaviors, child and parents' physical activity levels and parent weight at each time point. The coefficient θ will

IRB-HSR # 19748: A randomized-controlled trial to compare the reach, effectiveness and maintenance of two family-based childhood obesity treatment programs in a medically underserved region

capture the potential differences by treatment condition. For those discrete outcomes, appropriate link functions and distribution assumptions will be used in the modeling.

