Community Advisory Board

- Mixed-methods evaluation, quantitative survey and qualitative interview questions, pertaining to: communication, trust, decision making procedures, conflict resolution, group roles, problem assessment, collective efficacy, leadership, accomplishments and impact, participation and influence, community power, resources, sustainability, and overall satisfaction.
- This evaluation will occur annually, or at three time points, during the study.

Parent Advisory Team

- Mixed-methods evaluation, quantitative survey and qualitative interview questions, pertaining to: communication, problem assessment, collective efficacy, leadership, participation and influence, community power, overall satisfaction, and influence. Qualitative will also include questions pertaining to PAT's role to assist in family recruitment activities and to assist in family adherence by providing a program 'safety net'.
- This evaluation will occur annually, or at three time points, during the study.

3. Do you confirm that, except for blood draws through a peripheral site, that all invasive procedures will be performed by a licensed health care provider under the supervision of an MD?

There are no invasive procedures in this protocol.

4. Will you be using data/specimens in this study that were collected previously, with the use of a research consent form, from another research study?

No

5. Will any of the procedures listed in item # 2 have the potential to identify an incidental finding? This includes ALL procedures, assessments and evaluations that are being done for RESEARCH PURPOSES that may or may not be considered investigational.

It is possible that a subject's blood pressure reading would be out of the range of normal

X The examination(s) utilize(s) the same techniques, equipment, etc., that would be used if the subject were to have the examination(s) performed for clinical care. **There exists the potential for the discovery of clinically significant incidental findings.**

- The PI takes full responsibility for the identification of incidental findings:
- The PI will inform the subjects verbally of all incidental findings that are of clinical significance or are of questionable significance.
- A follow-up letter describing the finding should be provided to the subject with instructions to either show the letter to their PC or if the subject has no PCP, the subject should be instructed to make an appointment at UVa or at the Free Clinic.

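### Secondary Aim #2 does not say how missed board surveys are handled; repeated-measures ANOVA drops those members by default, and a linear mixed model would use every available survey

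*Combined protocol and SAP*

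**What the plan says.** All references are to the combined protocol and SAP.

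- **Method** (Statistical Considerations, item 5, Secondary Aim #2): "quantitative capacity dimensions will be analyzed using repeated measures ANOVA, accounting for differences between community and academic members". The paragraph gives no rule for a member who misses a survey.
- **Group sizes** (Subjects, item 1): "20 members of the Community Advisory Board" and "15 member of the Parent Advisory Team".
- **Attrition** (Subjects, item 2): "We anticipate approximately 10% attrition from both the Community Advisory Board and Parent Advisory Team". It is not said whether this is a total or a yearly rate.
- **Occasions** (Biomedical Research, item 2, for each group): "This evaluation will occur annually, or at three time points, during the study". The timeline in Subjects, item 5 has "mixed-methods evaluation at end of each study year".
- **Participation** (Brief Summary/Abstract): "those who volunteer and sign informed consent will also participate in annual mixed-methods evaluation to assess capacity and engagement". Twenty and 15 are therefore planned sizes that voluntary participation may reduce.
- **Hypothesis** (Hypothesis to be Tested): "community capacity for implementing and sustaining a locally relevant FBCO treatment and maintenance program will remain high over time". No threshold or margin is given.
- **Other analyses**: the primary aim (item 4) and Secondary Aim #3 (item 5) use multi-level mixed models. Item 2 lists last observation carried forward, Bayesian multiple imputation and Heckman-type selection models, in a paragraph about the parent/child assessments.

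**The concern.** The plan expects some board members to be lost, yet for this aim it names a method whose usual implementation discards all the surveys of anyone with one missing. In groups this small, each discarded member takes usable earlier surveys away.

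The content of the surveys adds to the worry. They cover matters such as trust, conflict resolution, influence and overall satisfaction. If members with a poorer view of the partnership are the ones who leave, the remaining members' average overstates capacity. The hypothesis is partly about level, so the handling of leavers could affect how the result reads.

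**Working it through.** The documents give no power, precision or sample-size figure for this aim, so there is nothing of the plan's own to reproduce.

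**1. Members left under complete-case analysis.** Inputs: 20 and 15 members and 10% attrition (Subjects, items 1 and 2), read as a total.
- CAB: 20 × 0.9 = 18.0
- PAT: 15 × 0.9 = 13.5, so 13 or 14
- If 10% were lost in each of the two intervals between surveys: 20 × 0.81 = 16.2 and 15 × 0.81 = 12.2

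**2. Level bias if the lowest first-year scorers leave.** Assumptions, none from the documents: normal scores with SD 1, equal correlation 0.6 between any two of a member's surveys, no true change, and exactly the lowest scorers lost. The year-1 mean of those who stay is too high by

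s = −(sum of the expected lowest k order statistics) / (n − k).

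At years 2 and 3 the excess is 0.6 × s, so the three-year average excess is s × (1 + 0.6 + 0.6)/3.

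| Group | Lost | s (year 1) | Years 2 and 3 | Average | Apparent change, year 1 to 3 |
|---|---|---|---|---|---|
| CAB, n = 20 | 2 | (1.867 + 1.408)/18 = 0.182 | 0.109 | 0.133 | −0.07 |
| PAT, n = 15 | 2 | (1.736 + 1.248)/13 = 0.230 | 0.138 | 0.168 | −0.09 |
| PAT, n = 15 | 1 | 1.736/14 = 0.124 | 0.074 | 0.091 | −0.05 |

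Simulation gives 0.13 SD for the CAB and 0.17 SD for the PAT with two lost. With correlation 0.3 or 0.8 in place of 0.6, the averages are 0.10 or 0.16 (CAB), 0.12 or 0.20 (PAT, two lost) and 0.07 or 0.11 (PAT, one lost).

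The last column matters. The completers' excess is largest in year 1 and then shrinks, so they appear to decline although nothing has changed.

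**3. Bias in the trend under other patterns.** Large-sample simulation: 100,000 members, correlation 0.6, true change from year 1 to year 3 of −0.40 SD, 10% missing. All of these except the 10% are assumed. Complete cases are compared with likelihood estimation from all available surveys (unstructured covariance).

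| Who is missing | Complete cases | All available surveys |
|---|---|---|
| Low at year 1, then leave | −0.46 | −0.40 |
| Low at year 2, then leave | −0.40 | −0.40 |
| Fell from year 1 to 2, then leave | −0.34 | −0.40 |
| Year 3 missing by chance | −0.40 | −0.40 |
| Year 3 missing because year 3 is low | −0.34 | −0.31 |
| Year 3 missing because of a fall from year 1 to 3 | −0.27 | −0.31 |

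Complete-case analysis can overstate a decline, understate it or leave it unchanged. Likelihood estimation is unbiased when missingness depends only on observed scores. In the last two rows, where missingness depends on the unseen score, it stays biased, and in one of them it is further off than complete cases.

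**4. Precision.** Smallest change between year 1 and year 3 detectable with 80% power (paired t-test, two-sided 0.05, correlation 0.6, all assumed for this aim): 0.59 SD with 20 members, 0.63 with 18, 0.70 with 15, 0.72 with 14 and 0.76 with 13. Keeping every member changes this by about 0.04 SD for the CAB and 0.02 to 0.06 SD for the PAT at most.

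**The case against.** **Complete-case analysis is not written into the plan.** That stands. A reader might infer that Aim #2 is restricted to members who answer every year, but this is the default of the method and not a statement in the text. The imputation list in item 2 might be thought to cover the gap. However, it sits among the parent/child assessments and is not tied to the boards. If it did apply, carrying the last observation forward would itself tend to hide a decline. The supportable statement is that the handling is unstated.

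**The direction of bias is not established.** A reader might infer that the planned analysis favours the hypothesis of sustained capacity. The documents do not say who will leave. Even if low first-year scorers leave, only the average level moves in the hypothesis's favour; the time effect in the ANOVA moves towards a spurious decline of 0.07 to 0.09 SD with two members lost.

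**The loss is small.** That stands: one or two members per group. A reader might suppose that 10% miss each of three surveys independently, leaving 20 × 0.9³ = 14.6 and 15 × 0.9³ = 10.9, but the plan's figure does not describe such a pattern.

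**The mixed model is not free of cost.** That also stands. With 15 to 20 members it needs a stated covariance and a small-sample degrees-of-freedom method, and it does not remove bias when missingness depends on the unobserved score.

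**The ANOVA is not the only evidence.** Aim #2 also rests on interviews. This limits the consequence but leaves the survey analysis unspecified.

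**Conclusion.** The point holds as a minor, cheap improvement. Aim #2 expects some loss of members, states no handling of missed surveys, and names a method that by default drops anyone with one missing. At the plan's own attrition figure, read as a total, about 18 of 20 CAB and 13 to 14 of 15 PAT members remain.

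The size depends on assumptions. If exactly the lowest first-year scorers leave and the within-member correlation is 0.6, the completers' average level is too high by about 0.13 SD (CAB) and 0.09 to 0.17 SD (PAT, one or two lost). These are upper values for that pattern, because less selective departure gives less. The bias in the trend has no fixed sign.

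The documents do not support saying that the analysis is tilted towards confirming the hypothesis, or that a mixed model costs nothing. Nor does the model settle what counts as staying high: with no threshold or margin, a non-significant time effect in groups of this size could be read as support under either method.

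**What to change.** In Secondary Aim #2, replace the repeated-measures ANOVA with a linear mixed model fitted to all available surveys:

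- a random intercept for each member and year as a categorical factor;
- for the CAB only, community/academic group and its interaction with year (the PAT is made up of parents, so the factor has no clear meaning there);
- a small-sample degrees-of-freedom correction such as Kenward–Roger.

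Report the number responding each year and the yearly means with 95% confidence intervals.

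The cost is a short change of wording, with no new data or staff, and the approach matches the mixed models already planned for the primary aim and Secondary Aim #3. The limits should be stated with it: the model assumes data missing at random, does not remove bias when the unobserved score drives the absence, and adds little power at 10% attrition.
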